2.3.2. Known Potential Benefits of Trial Interventions

As described above, demonstrated benefits of CBT-based interventions in the non-ESRD setting include reduced pain interference and pain intensity, reduced opioid use, and improved quality of life. In the ESRD setting, CBT has been shown to be an effective treatment for depression.⁴⁶ Buprenorphine improves function and quality of life in individuals with opioid dependence and has demonstrated analgesic efficacy. Buprenorphine has a markedly lower risk of overdose compared to full agonist opioids so its use could decrease long-term overdose risk.

2.3.3. Assessment of the Balance between Risks and Benefits

Risks of the trial interventions, described above, are similar to those in routine clinical care. Benefits and risks of recommended therapies will be discussed with patients as in clinical practice. To address the potential for increased distress from discussing sensitive topics in the PCST arm, the PCST coaches will be trained to manage such distress in accordance with accepted standard practices, and there will be a protocol in place for protective transfer should greater intensity of services be indicated. Buprenorphine is an FDA-approved medication for which there is more than 15 years of post-marketing data, and a risk profile that is similar among patients with and without impaired kidney function. Buprenorphine is a schedule III controlled substance, meaning its risk for abuse is considered by the DEA to be lower than the risk with the opioid medications likely to be used by patients enrolled in the trial (mostly schedule II opioids). Eligibility for the buprenorphine component of the trial intervention will be based on specific criteria assessed at Week 24 and use of buprenorphine will require additional informed consent.

Overall, the benefits of trial participation outweigh the risks based on the following considerations: 1) there are substantial potential benefits including improved pain management, decreased opioid-related adverse effects, and improved safety, and 2) the known risks will be minimized through individualized care decisions consistent with standards of care.

3. STUDY OBJECTIVES

The overall objective of the trial is to evaluate the effectiveness of approaches to reducing pain and opioid use among individuals receiving treatment with maintenance hemodialysis for ESRD. The specific objectives and outcomes are summarized in **Table 3.1**. Additional information about the outcomes and methods for their ascertainment is provided in **Section 4.3**.

Table 3.1. Trial Objectives and Outcomes

Objectives	Outcomes	Justification for Outcomes
Primary		
To evaluate the effectiveness of pain coping skills training compared with usual care for reducing pain interference, opioid use, and related outcomes among patients with end-stage renal disease receiving treatment with maintenance hemodialysis	
The primary outcome is reduction in pain interference, as measured by the Brief Pain Inventory Interference scale.
 
Secondary outcomes include:
 
• Pain intensity• Composite of pain interference and opioid use• Opioid use• Pain catastrophizing• Quality of life• Depression• Anxiety• Coping• Self-efficacy• Sleep quality• Fatigue• Other symptoms• Satisfaction with treatment• Social support• Family intrusion• Discrimination• Falls• Hospitalization rate• Death	
The primary outcome, pain interference, is important both patients and providers, and has been recommended by expert consensus groups as one of the most important measures for chronic pain trials.
 
The secondary outcomes include conditions or symptoms often associated with chronic pain and/or opioid use, or clinical events that can result from medications used to manage pain.

Exploratory		
To explore acceptability, tolerability, and efficacy of buprenorphine among hemodialysis patients receiving moderate to high-dose long-term opioid therapy for chronic pain	
• Acceptability to patients, as measured by the proportion of participants who initiate buprenorphine from among those participants who are offered buprenorphine.• Tolerability, as measured by the proportion of participants who do not discontinue buprenorphine due to adverse effects or intolerance.• Efficacy, as assessed by the Brief Pain Inventory Interference scale	Assessment of acceptability and tolerability of buprenorphine is needed before conducting definitive large scale trials of buprenorphine in the hemodialysis patient population.

4. STUDY DESIGN AND OUTCOMES

4.1. Trial Design and Rationale

The primary trial hypothesis is that pain coping skills training will improve pain and opioid use outcomes more than usual clinical care. The design is a multicenter, sequential, multiple assignment trial with a randomized component (Phase 1) and a non-randomized component (Phase 2). In Phase 1 (Weeks 1 - 24), participants will be randomized into one of two treatment groups: 1. Pain Coping Skills Training (PCST) for 24 weeks, or 2. Usual Care. The PCST intervention has two sequential components each taking place over 12 weeks: 1) weekly telehealth sessions with a PCST coach, and 2) daily interactive voice response (IVR) sessions via telephone. The primary outcome of pain interference will be ascertained at Week 12 which coincides with the end of the PCST weekly coaching sessions. In Phase 2, beginning at Week 24, participants in both randomized groups will be assessed for eligibility for a second intervention, buprenorphine, as an alternative to full agonist opioid pain medication. The main eligibility criterion for the buprenorphine intervention is current use of prescribed opioids at an average dose of \geq 20 morphine milligram equivalents (MME)/day. Participants who meet the buprenorphine eligibility criteria will be encouraged, but not required, to switch from their current opioid medication to buprenorphine to explore buprenorphine as an approach to addressing physical opioid dependence in patients receiving maintenance hemodialysis. Participants who do not meet the buprenorphine eligibility criteria will not be offered buprenorphine. All participants will continue to be followed from Week 24 until Week 36 (Phase 2) for ascertainment of pain, opioid use, and other outcomes to address durability of the effects of PCST, and, for those who switched to buprenorphine, to assess buprenorphine acceptability, tolerability, and efficacy as exploratory outcomes.

Randomization will be performed at the level of the individual participant using permuted blocks with stratification by enrolling site and by the presence or absence of opioid use using the criteria provided in **Section 5.3** for the Phase 1 randomization. Treatment assignments will not be masked to participants or research team members because of 1) impracticability, and 2) an interest in implementing the interventions as they would be outside of a trial setting. The trial includes a control group that does not receive an active intervention beyond usual clinical care so it is possible to determine whether changes observed in the active treatment groups are the result of the interventions or the result of either increased attention that accompanies trial participation or the natural history of the condition. Bias will be minimized by performing randomization after collection of baseline data, concealing the allocation order, and ascertaining the patient-reported outcomes, including the primary outcome, using standardized, centrally administered questionnaires by research personnel blinded to treatment assignment. Safety and tolerability will be evaluated through ascertainment of specific adverse events of interest and serious adverse events throughout the duration of the trial.

4.2. Outcomes

Citations and references for the instruments or questionnaires used for the outcome ascertainment are provided in **Appendix 14.2** and **Section 13**, respectively.

4.2.1. Primary Outcome: Pain Interference

Pain interference will be measured by the Brief Pain Inventory Interference Scale (BPI Interference)⁴⁷ which has a 7-day look-back period. The BPI is a multidimensional measure developed for cancer pain, but subsequently validated in diverse populations, including patients with chronic pain.^{47, 48} BPI is composed of the severity subscale (four pain intensity items) and the interference subscale (seven pain interference items). Pain interference has been recommended by expert consensus groups as a key outcome measure in chronic pain trials.⁴⁹ Interference, or the degree to which pain interferes with various domains of function, is thought to have greater salience with patients and greater generalizability across populations than pain intensity.^{47, 50-53} The BPI Interference scale, specifically, has demonstrated responsiveness to change in numerous clinical trials.⁵⁴⁻⁵⁶

4.2.2. Secondary Outcomes

The secondary outcomes will include: 1) patient-reported indicators of pain and opioid use, 2) patient-reported indicators of conditions or symptoms that often accompany pain and/or opioid use, 3) clinical outcomes, and 4) acceptability and tolerability outcomes.

4.2.2.1. Secondary Pain and Opioid Use Outcomes

As secondary outcomes, pain and opioid use will be assessed using the instruments or methods shown in **Table 4.1** and analyzed as continuous measures.

Table 4.1. Secondary Outcomes: Pain and Opioid Use

Domain	Instrument or Data Source	Look-Back Period	Time-Points for Assessment
Pain intensity	Brief Pain Inventory (BPI) Severity	7 days	Weeks 0, 12, 24, 36
Pain catastrophizing	Pain Catastrophizing Scale – SF 6	None	Weeks 0, 12, 24, 36
Opioid use	Timeline Followback	14 days	Weeks 0, 12, 24, 36
Composite of pain and opioid use	BPI Interference / Timeline Followback	7 days/14 days	Weeks 0, 12, 24, 36

4.2.2.1.1. Composite Outcome of Pain and Opioid Use

One of the secondary outcomes is a composite outcome of pain and opioid use as shown in **Table 4.2**. Both a reduction in pain interference with stable or decreased opioid use, and a reduction in opioid use with stable or decreased pain interference will be categorized as success.

Table 4.2. Composite Outcome of Pain Interference and Opioid Use: Success (+) or No-Success (-)

	Pain Less	Pain Stable	Pain More
Opioid Use Less	+	+	-
Opioid Use Stable	+	-	-
Opioid Use More	-	-	-

Criteria for Less, Stable, and More Pain

For the composite outcome of pain and opioid use, the criteria for less, stable, and more pain are based on the change from the baseline BPI Interference score using the following thresholds:⁵⁷

Pain Less: Decrease in BPI Interference score of > 1 point

Pain Stable: Change in BPI Interference by 0 – 1 point in either direction

Pain More: Increase in BPI Interference by > 1 point

Criteria for Less, Stable, and More Opioid Use

For the composite outcome of pain and opioid use, the criteria for less, stable, and more opioid use are based on the difference from baseline in average MME/day using the following thresholds:

Opioid Use Less: ≥ 25% reduction in average MME/day

Opioid Use Stable: < 25% reduction and < 10% increase in average MME/day

Opioid Use More: ≥ 10% increase in average MME/day

The rationale for considering an increase in MME/day of up to < 10% as stable opioid use is to account for sporadic, unpredictable acute pain events or clinically unimportant increases in chronic opioid use.

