5.3. Subgroup with Current or Recent Opioid Use

During eligibility screening all potential participants will have opioid use ascertained using the timeline follow back approach. The trial will enroll at least 300 participants (among the 640 total study participants) with current or recent opioid use defined as patient-reported prescription opioid use during at least 3 of the past 6 months. The number of participants in the opioid use subgroup will be monitored throughout the trial enrollment period. If the rate of enrollment into the opioid use subgroup is lower than targeted, trial enrollment will be restricted to individuals meeting the opioid use criteria as long as this restriction will not compromise the ability of the trial to meet its overall enrollment goal by the target completion date.

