10.2.3.2 Analyses of the Secondary Endpoints

The secondary endpoints include pain severity, pain catastrophizing, opioid use, other PROs, hospitalizations, falls and mortality.

For continuous endpoints, such as pain severity, pain catastrophizing, and opioid use expressed as MME/day., similar methods as described for the primary outcome will be used to compare differences in changes of the endpoints between PCST and Usual Care at 12 (**Table 10.1; Question 1**), 24 (**Table 10.1; Question 2**), and 36 (**Table 10.1; Question 3**) weeks; i.e., linear mixed effects models with adjustment for baseline measures (and additional adjustment for buprenorphine eligibility and initiation of buprenorphine for **Question 3 in Table 10.1**), taking into account the repeated measures over time and clustering of recruitment sites via random effects.

For binary endpoints, such as the composite of pain interference and opioid use, generalized linear mixed effects models with a binomial distribution and a log link adjusting for baseline measures (additionally adjusting for buprenorphine eligibility and initiation of buprenorphine for **Question 3 in Table 10.1**), taking into account the repeated measures over time and clustering of recruitment sites via random effects, will be used to compare relative risks between PCST and Usual Care at 12 (**Table 10.1; Question 1**), 24 (**Table 10.1; Question 2**), and 36 (**Table 10.1; Question 3**) weeks.

For recurrent endpoints (counts) such as number of hospitalizations and falls, participants will be followed from baseline to 36 weeks, loss-to-follow-up, or death, whichever comes first. Generalized linear mixed effects models with a Poisson distribution, an offset of follow-up time and a log link adjusting for baseline measures (additionally adjusting for buprenorphine eligibility and initiation of buprenorphine for **Question 3 in Table 10.1**) will be used to compare event rates between PCST and Usual Care during the Phase 1 study period (**Table 10.1; Questions 1 – 3**). Repeated measures over time and clustering of recruitment sites will be taken into account via random effects.

For time to event endpoints such as mortality, participants will be followed from baseline to 36 weeks, loss-to-follow-up, or death, whichever comes first. Cox proportional hazards models will be used to compare risks of

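### The pain-and-opioid composite has no rule for a zero opioid baseline, and its 10% allowance for sporadic use is nil for non-users and slight for low-dose users

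*Combined protocol and SAP*

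**What the plan says.** In Section 4.2.2.1.1 the opioid half of the composite is "based on the difference from baseline in average MME/day using the following thresholds", and every one of those limits is a percentage of the baseline value. Less is a "≥ 25% reduction in average MME/day". A rise of 10% or more is classed as More, and whatever falls between these two limits is Stable.

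The section explains that small increases count as stable "to account for sporadic, unpredictable acute pain events or clinically unimportant increases in chronic opioid use". Table 4.1 gives opioid use a 14-day look-back. In Table 4.2, opioid use rated More is no-success whatever happens to pain, and Stable opioid use is success only with Pain Less.

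On who is in the trial, Section 5.3 says: "The trial will enroll at least 300 participants (among the 640 total study participants) with current or recent opioid use". It defines such use as patient-reported prescription use in at least 3 of the past 6 months. Section 4.1 makes presence or absence of opioid use a randomisation stratum, and Section 6.1 gives PCST separate motivational content for people without opioid use. Section 10.2.3.2 models the composite as a binary endpoint without restricting it to users, and Section 10.6 includes all randomised participants in the Phase 1 analyses. No section gives an absolute MME threshold or a rule for a baseline of zero.

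**The concern.** A percent change needs a positive baseline, and a large part of this trial is recruited from people who may not have one. Two things follow.

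First, the category of a participant who takes no opioids at either time point is not defined by the written rule, so it has to be chosen at analysis. Second, the tolerance scales with the baseline. Ten percent of nothing is nothing, so the participants for whom a single acute dose is most plainly sporadic get no allowance at all, contrary to the purpose that the section states. Such a participant is scored no-success even when pain interference has clearly improved.

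What is at stake is the meaning and the success rate of one secondary endpoint, and whether its coding is fixed before results by arm are seen.

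**Working it through.** **Inputs.** The 25% and 10% thresholds and the 1-point pain threshold come from Section 4.2.2.1.1. The 14-day window comes from Table 4.1, and 640 and the minimum of 300 from Section 5.3. The SDs of change in BPI Interference, 2 and 3, are those of Table 10.2. Assumptions for illustration: a normal distribution of change; a mean change of 0 or -0.62 (the latter borrowed from Table 10.2, row 2); a low-dose baseline of 5 MME/day. The documents give no event rate or power for the composite, so there is no stated figure to reproduce.

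**1. Size of the no-use stratum.** 640 - 300 = 340, or 340/640 = 53%, if the minimum is just met.

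**2. The rule at baseline zero.** Percent change = 100 × (F - B)/B, with B the baseline and F the follow-up average MME/day. With B = 0 this is 0/0 when F = 0 and has no finite value when F > 0. Rewriting to avoid the division does not help. Less becomes F ≤ 0.75B and More becomes F ≥ 1.10B, with Stable in between. At B = F = 0, Less and More are both satisfied and Stable is not. At B = 0 and F > 0, only More is satisfied.

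**3. Size of the allowance.** The increase that triggers More over the window is 0.10 × B × 14.

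- B = 0: 0 MME.
- B = 5 MME/day: 0.10 × 5 × 14 = 7 MME in total.
- In equal-sized doses, one extra dose on top of k baseline doses is a 100/k percent increase. That is 10.0% at k = 10 (More) and 9.1% at k = 11 (Stable). Anyone with 10 or fewer doses in the baseline window therefore has no room for one more.

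**4. Effect on the composite of one sporadic dose.** By Table 4.2, moving a participant from Stable to More alters the result only if pain is rated Less, that is, a change below -1. The share is Φ((-1 - mean)/SD).

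| Mean change | SD | Share with Pain Less | Out of 34 |
|---|---|---|---|
| 0 | 2 | 0.3085 | 10.5 |
| 0 | 3 | 0.3694 | 12.6 |
| -0.62 | 2 | 0.4247 | 14.4 |
| -0.62 | 3 | 0.4496 | 15.3 |

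The last column takes 34 non-users with such a dose, which would be one in ten of a stratum of 340. About 10 to 15 go from success to failure. The other 19 to 24 fail under either coding, because Stable opioid use without Pain Less is already no-success.

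**5. Why zero to zero should be stated.** Suppose, as an extreme case, that 340 participants start and stay at zero, with mean pain change 0. Coded Stable, successes are 340 × 0.3085 = 105 (SD 2) to 340 × 0.3694 = 126 (SD 3). Coded Less, Pain Less or Pain Stable suffices, with share Φ(1/SD): 340 × 0.6915 = 235 (SD 2) or 340 × 0.6306 = 214 (SD 3). Coded More, there are none.

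**The case against.** The opening of Section 4.2.2.1.1 counts less pain with stable or decreased opioid use as success, and going from no use to no use is stable in ordinary language. Most analysts would code it so. That is a fair reading and the one adopted here, but the thresholds do not say it, and one sentence would settle it.

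It can also be argued that the allowance is deliberately relative, and that counting any new opioid use in a non-user as More is a defensible, conservative choice in a trial that aims to reduce opioid use. It would be defensible if the plan had chosen it. The plan's stated reason for the allowance points the other way, and nothing shows that loss of the allowance at zero was intended.

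A reader might infer that 340 participants have a zero baseline, or that more than half of the trial drops out of this endpoint. The documents support neither. The 300 is a minimum, not a cap. The stratum rests on a 6-month history, whereas the composite uses 14 days. Occasional users outside the opioid stratum may have a positive baseline, members with recent use may have none in the window, and Section 7.3 lets randomisation run past 640. The true count may be lower or higher than 340. Nor does any section suggest excluding non-users.

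A reader might also take every non-user with one dose as a failure caused by the rule. Step 4 shows that this overstates it, since most of them would not have been successes anyway.

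**Conclusion.** The concern holds for this one secondary outcome and should be corrected. The composite has no zero-baseline rule although non-users are in the trial and in its analysis by design, and its tolerance for sporadic use vanishes for them and nearly vanishes at low baselines. Under the assumed pain changes, 31% to 45% of non-users who take a sporadic dose in the window would be reclassified from success to failure. How many would take such a dose, and how many have a zero baseline, the documents do not say.

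On the natural reading, a participant with a zero baseline cannot reach Less and can succeed only through Pain Less. A pooled success rate therefore mixes two routes to success for users with one for non-users. Section 10.2.2 adjusts for opioid use, but Section 10.2.2.2 does not name it among its example subgroup factors.

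It would be wrong to extend the criticism to the analysis of "opioid use expressed as MME/day" in Section 10.2.3.2. A difference in mean change over all randomised participants is well defined at zero and is a legitimate intention-to-treat contrast. The primary BPI Interference analysis is likewise untouched.

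**What to change.** Before unblinding, amend the composite definition and its reporting in three respects:

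1. State that zero at baseline and zero at follow-up is Stable.
2. Add one absolute MME/day tolerance, with its value set by the trial team. At a zero baseline, classify by that tolerance alone: an increase within it is Stable and one above it is More. At a positive baseline, call an increase More only if it is at least 10% and also above the tolerance; smaller increases are Stable. The definition of Less stays as it is. Using the tolerance alone at zero matters, because a rule that still required a 10% increase there would remain undefined.
3. Report the composite within each opioid-use randomisation stratum as well as overall. MME/day may be tabulated by stratum as supportive information. The strata are not identical to zero and positive 14-day baselines, so the number of zero baselines in each should be shown.

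The cost is a few lines of SAP text and one further tabulation. The one real demand is that a tolerance value be agreed and justified before results by arm are known.

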4.2.2.2. Secondary Outcomes Reflecting Conditions or Symptoms Associated with Pain and/or Opioid Use

The effects of the interventions on several conditions or symptoms often associated with pain and/or opioid use will be evaluated through ascertainment of a set of patient-reported outcomes using validated instruments (see **Table 4.3**).

Table 4.3. Secondary Outcomes Reflecting Conditions or Symptoms Associated with Pain and/or Opioid Use

Domain	Instrument or Data Source	Time-Points for Assessment
Depression	Patient Health Questionnaire (PHQ)-9	Weeks 0, 12, 24, 36
Anxiety	Generalized Anxiety Disorder (GAD)-7	Weeks 0, 12, 24, 36
Sleep quality	PROMIS Sleep Disturbance 6a + Sleep Duration Question	Weeks 0, 12, 24, 36
Fatigue	PROMIS Fatigue SF 6a	Weeks 0, 12, 24, 36
Other symptoms	Dialysis Symptom Index	Weeks 0, 12, 24, 36
Physical functioning	PROMIS Physical Functioning SF 6b	Weeks 0, 12, 24, 36
Quality of life	Single-Item QOL Scale [SIS] from McGill Quality of Life (MQOL)	Weeks 0, 12, 24, 36
Coping	Coping Strategies Questionnaire: 1-item version	Weeks 0, 12, 24, 36
Self-efficacy	PROMIS Self-Efficacy for Managing Chronic Conditions – Managing Symptoms – Short Form 8A + single item targeting self-efficacy for pain	Weeks 0, 12, 24, 36
Discrimination	Everyday Discrimination Scale	Weeks 0, 36
Satisfaction with treatment	Patient Global Impression of Change	Weeks 0, 12, 24, 36
Family intrusion	PROMIS Satisfaction with Social Roles and Activities	Weeks 0, 12, 24, 36
Social support	Multidimensional Scale of Perceived Social Support (MSPSS)	Weeks 0, 12, 24, 36

